This project will use an efficient 2x2x2x2 factorial design (Table 1) to identify reach-focused intervention components that either singly, or in combination, increase patient use of evidence-based smoking cessation treatment over 2 years of availability and, by extending treatment reach, reduce smoking prevalence 2 years after enrollment. All adult patients who smoke daily, but who are **not willing to enter smoking cessation treatment** at the time of enrollment (the vast majority of smokers⁴⁰) will be eligible to participate, with no obligation to quit smoking or use treatment. Participants (N=240-300) will be recruited in 4-12 primary care clinics in 2 healthcare systems by system staff using an opt-out strategy⁴¹ to maximize inclusion and enhance dissemination and the generalizability of results. (Roughly 60 additional patients who do not meet eligibility criteria for intensive counseling and medication with either combination NRT or varenicline will be included in the study but will not be part of the experimental sample.)

This will be the first factorial experiment in healthcare settings to test interventions designed to extend the reach of varied smoking cessation treatments in primary care patients who are not initially willing to make an aided quit attempt (see Table 1). This rigorous and efficient factorial design will address the following aims:

Primary Aims

1. To **create an optimized reach intervention package** by identifying intervention components that increase cessation treatment reach especially well, at low cost, at 1-year follow-up.
2. To estimate the **main and interactive effects** of the intervention components on cumulative treatment **reach over 2 years** of treatment access.

Secondary Aims

1. To estimate the main and interactive effects of intervention components on **abstinence** at 2-year follow-up.
2. To identify the degree to which intervention component effects on 2-year abstinence are **mediated by increases in cessation treatment reach**.
3. To assess the **cost-effectiveness** of intervention components in promoting reach and abstinence.
4. To identify patient and clinic **moderators** of intervention component effects on reach and abstinence.

III. METHODS

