Design Overview. In this factorial experiment (see Table 1), participants (not willing to enter cessation treatment at the time of enrollment) recruited by phone after initial outreach or primary care visits in or telemedicine appointments with participating clinics in UW Health and AdvocateAurora Health will be screened, consented, and randomized over the phone to one of 16 conditions resulting from the crossing of the 4 experimental factors in this 2 (incentives on vs. off) x 2 (tailored vs. generic outreach letters) x 2 (care manager calls on vs. off) x 2 (access to intensive treatment on vs. off) design. Participants who request treatment for smoking cessation over the next 2 years will do so through a Tobacco Care Manager who will coordinate referrals to a tobacco quitline (the Wisconsin Tobacco Quit Line (WTQL) for Wisconsin residents) and/or the patient's primary care provider, as preferred by the patient in the standard care conditions. Tobacco Care Managers will also coordinate scheduling with a UW-CTRI Health Counselor for intensive smoking cessation treatment. Participants will have access to either standard or intensive smoking cessation treatment for 24 months, and will receive outreach promoting smoking cessation twice per year from enrollment to 22 months post-enrollment. Participants will be asked to complete brief (10-20-minute) follow-up telephone interviews 6, 12, 18, and 24 months after enrollment. Those claiming abstinence at the 12- and 24-month post-enrollment phone interviews will be asked to return to their primary care clinic to complete breath, urine, and/or saliva testing to verify abstinence from combustible tobacco. This will entail providing breath samples for carbon monoxide testing and/or a urine or saliva sample for immediate cotinine/anabasine testing (no samples will be stored). Participants may also be asked to collect a saliva sample at home and return it in the mail. If a participant sets a target stop-smoking date as part of a smoking cessation treatment episode (either standard or intensive treatment), the participant will be asked to complete telephone follow-up interviews 3, 12, and 26 weeks post-target-quit-day, as well. Participation in the study will last 24 months (27 months maximum, if the person is not reached immediately for the final 24-month post-enrollment telephone follow-up or visit). In addition, data on health status and healthcare utilization for participants who do vs. do not use stop-smoking treatment and quit smoking will be extracted from the EHR for up to 1 year pre-enrollment, and 4 years post-enrollment to inform economic analyses for Aim 3 and moderation analyses for Aim 4.

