Secondary Aim 3. We will attempt to estimate total (service, administrative, medication, utilization, patient out-of-pocket) costs of implementing the reach interventions in the study (e.g., costs related to administration, training, supervision, recruitment, medication screening) and each specific intervention component (and combination thereof) as tertiary outcomes for the project, without including any costs related only to research activities. First-year and second-year costs will be estimated separately in order to generate cost estimates after 1 year of implementation (and compare these with program costs of the usual fax-to-quit care approach in place prior to study launch), and to separately estimate program maintenance costs. To generate stable estimates of short and longer-term costs and savings, we will extract data on healthcare utilization from 1 year pre-enrollment to up to 4 years post-enrollment (maximum of 5 years total). These tertiary analyses will inform optimization of health system reach interventions and provide healthcare systems that may adopt reach interventions estimates of both initial and maintenance costs, overall, and by intervention component. We will compute total costs, and costs by category, and then use these cost data to compute cost per treatment initiation (the primary outcome of this study), cost per quit (the secondary, abstinence outcome), and costs per Quality Adjusted Life Years gained (QALYs⁶⁷) by each intervention component. These analyses will help to assess intervention component efficiency in terms of promoting reach, abstinence (effectiveness), and quality of life. We may also conduct exploratory analyses to estimate net monetary benefit (NMB) when considering the added costs of the reach intervention components, and the monetized value of their QALYs gains. In addition, we may use incremental cost-effectiveness ratios (ICERs)^{68,69} to assess intervention component efficiency in promoting reach, and, separately, abstinence. These exploratory cost-effectiveness methods will be computed in the primary sample of participants eligible for intensive treatment access, where the costs of standard care and both forms of intensive treatment will be

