computed and analyzed. We will conduct an exploratory replication of these cost-effectiveness analyses in the sample of patients eligible only for standard care who may differ systematically from those eligible for intensive treatment. In addition, we will use EHR-extracted data on healthcare utilization for participants who do vs. do not use smoking cessation treatment, and those who do vs. do not quit smoking to estimate potential savings resulting from implementation of each reach intervention (and combination of interventions) in exploratory analyses. We may also conduct probabilistic sensitivity analyses across a range of assumptions to account for uncertainty^{70,71}. Healthcare system budget impact analyses may be conducted to help healthcare systems gauge the affordability of the most promising, cost-effective reach interventions⁷². This analysis will use data extracted from the EHR and from UW-CTRI research databases regarding intervention delivery and external estimates of Medicaid costs of healthcare system staff time and procedures.

Secondary Aim 4. To explore moderators of reach intervention responses, we will introduce individual differences (sex, age, race/ethnicity, education, insurance type, time-to-first-cigarette, quitting history, chronic conditions, healthcare utilization in the year prior to enrollment, and mental illness history) to the models described above for Aims 1-3. In addition to testing interactions between candidate moderators and reach intervention component main and interactive effects in logistic regression models of treatment use and abstinence, we may conduct regression tree analyses to identify subpopulations of smokers defined by compound characteristics that differ maximally on treatment initiation and abstinence outcomes and subgroups that vary in intervention response. These exploratory analyses can help to identify patients that may benefit especially from particular reach intervention components or combinations thereof. These analyses will use data collected at baseline, follow-up, and via the EHR.

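### The exploratory savings analysis attributes savings to each reach intervention using utilization differences between self-selected treatment users or quitters and everyone else

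*Combined protocol and SAP*

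**What the plan says.** The last part of Secondary Aim 3 in the Analysis Plan sets out the savings analysis. It states: "we will use EHR-extracted data on healthcare utilization for participants who do vs. do not use smoking cessation treatment". It then adds the second grouping and the target: "those who do vs. do not quit smoking to estimate potential savings resulting from implementation of each reach intervention". The sentence closes by extending the target to combinations and giving the status: "and combination of interventions) in exploratory analyses".

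The Design Overview under Methods describes the extraction for Aim 3 with the same grouping: "data on health status and healthcare utilization for participants who do vs. do not use stop-smoking treatment and quit smoking will be extracted".

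Two other statements fix what is and is not randomized. Goals/Aims says that participants join "with no obligation to quit smoking or use treatment". The Design Overview says that they are "randomized over the phone to one of 16 conditions resulting from the crossing of the 4 experimental factors".

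For timing, Secondary Aim 3 says "we will extract data on healthcare utilization from 1 year pre-enrollment to up to 4 years post-enrollment", so a baseline year of utilization is available for each participant.

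The Covariates paragraph provides for every model to be reported both with and without adjustment, and for covariates that are not significant predictors of the outcome to be dropped. It lists smoking-related comorbidity and use of healthcare among the known correlates of engaging with treatment.

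**The concern.** The target is causal and specific to each component: what a health system would save by implementing a given intervention. The utilization input is a difference between groups that participants sort themselves into after randomization. People who take up treatment or stop smoking may be sicker and in more frequent contact with care, or healthier and more motivated. Either pattern shifts later utilization whatever the interventions do. The plan's own Covariates paragraph names comorbidity and healthcare use as correlates of treatment engagement, and both plausibly drive later utilization too.

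The plan gives no causal method for this contrast and no rule for turning a per-user or per-quitter difference into savings per intervention. At stake is whether a figure labelled as a saving caused by a component, or a loss, could have its sign and size set by who chose treatment.

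**Working it through.** **What the text supports.** The plan states no standard deviation, cost, precision or power for the savings analysis, so there is no planned figure to reproduce. Setting the sections side by side:

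- Randomized: incentives, letters, care manager calls, access to intensive treatment.
- Compared for savings: use versus non-use of treatment, and quitting versus not quitting.
- Attributed to: each intervention and combination.

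The link between the second and third lines is not given.

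**How large selection alone could be.** All inputs here are assumptions except the 8-point increment, which the Power and Sample Size section uses for reach. Assume:

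- a baseline factor with odds ratio 1.5 to 2.0 per SD for treatment use and correlation 0.1 to 0.5 with utilization;
- base uptake of 10% or 30%;
- a component that raises uptake by 8 points;
- no effect of component or treatment on utilization.

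A simulation of 2,000,000 participants per setting gave:

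| Odds ratio | Correlation | User minus non-user (SD), base 10% / 30% |
|---|---|---|
| 1.0 | 0.1 to 0.5 | 0 within simulation error |
| 1.5 | 0.1 | 0.037 / 0.038 |
| 1.5 | 0.5 | 0.195 / 0.194 |
| 2.0 | 0.1 | 0.064 / 0.065 |
| 2.0 | 0.5 | 0.321 / 0.313 |

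A hand check is correlation × ln(odds ratio): 0.1 × 0.405 = 0.041 and 0.5 × 0.693 = 0.347, close to the simulated extremes. In every setting the randomized on-minus-off difference was at most 0.003 SD, which is simulation error around zero. Reversing the direction of selection reverses the sign of the gap.

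**Per participant.** If the per-user gap were multiplied by the 8-point rise in uptake:

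- 0.08 × 0.037 = 0.003 SD
- 0.08 × 0.321 = 0.026 SD

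In dollars, a separate illustration with an assumed noise SD of $5,000 gave a per-user gap of about $300 to $1,100. This becomes 0.08 × 300 = $24 to 0.08 × 1,100 = $88 per participant.

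**Precision of the as-randomized contrast.** With half of N at each level of a factor, the 95% half-width is 1.96 × √(2/(N/2)) in SD units:

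- N=240: 1.96 × √(2/120) = 1.96 × 0.129 = 0.253 SD
- N=300: 1.96 × √(2/150) = 1.96 × 0.115 = 0.226 SD

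Adjustment for prior-year utilization with correlation ρ multiplies these by √(1−ρ²). At an assumed SD of $10,000 and N=300:

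- unadjusted: $2,263
- ρ=0.5: 2,263 × 0.866 = $1,960
- ρ=0.7: 2,263 × 0.714 = $1,616

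The two dollar illustrations assume different SDs, so they should not be set against each other directly. All half-widths are before any loss of data.

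**The case against.** **Two-step reading.** A user or quitter contrast cannot by itself yield a figure for each component. The sensible reading is that it will be combined with the component effects on reach and abstinence, which are estimated as randomized. A reader might infer that the savings analysis, or Aim 3 as a whole, ignores the randomization. The documents do not support that. The two-step calculation is not excluded, and the other Aim 3 outputs (cost per initiation, per quit and per QALY) are organized by component. Utilization is also listed, undefined, among the costs to be totalled by component. This limits the point but does not remove it, because the saving per user or per quitter would still be observational.

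**Small bias, imprecise replacement.** The scaled bias is small, and the as-randomized half-width at N=300 is about 9 times its upper illustrated value (0.226/0.026) and 75 times its lower one (0.226/0.003). This is fair: the randomized estimate may not separate savings from losses. But scaling shrinks any true per-user saving by the same 0.08, so the bias relative to the saving, and the risk of a wrong sign, do not change. The July 2022 sample-size update already accepts effect sizes with ranges in place of powered tests.

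**Adjustment is available.** The Covariates paragraph, and Secondary Aim 4's use of prior-year utilization as a moderator, could reduce measured confounding. No model is specified for savings, so it is unclear whether they apply. Covariates can be dropped on significance, and unmeasured motivation and health behavior would remain.

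**Consequence.** A reader might infer that these savings figures are promised to health systems considering adoption. Secondary Aim 3 does say that the utilization data serve estimates of costs and savings, and that its tertiary analyses will inform optimization. What it undertakes to give adopting systems, however, is initial and maintenance cost estimates. The savings are called potential and are confined to exploratory work.

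**Conclusion.** The point holds in a limited form. The utilization input to the exploratory savings analysis is a confounded comparison of self-selected groups. Neither optional covariate adjustment nor multiplication by randomized uptake or abstinence effects makes the result a saving caused by an intervention. Its sign and size can reflect selection alone.

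The amount of bias is unknown. The range of 0.04 to 0.32 SD per user, or 0.003 to 0.026 SD per participant at an 8-point rise in uptake, rests on the assumed odds ratios and correlations, and it is zero if there is no self-selection. The dollar figures are illustrations only. The per-user gap must not be read as the error in savings per intervention, which would be much smaller under the two-step reading.

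Severity is low. The analysis is exploratory and tertiary, and the primary reach analyses and the abstinence analysis are unaffected.

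**What to change.** 1. Add to Secondary Aim 3 a regression of utilization cost on the randomized factors, including every randomized participant whether or not they used treatment or quit (for the intensive-treatment factor, everyone randomized on it). Adjust for pre-enrollment-year utilization and exempt that covariate from the significance-based removal rule.
2. Report this contrast, with its interval, as the estimate of savings caused by each component.
3. Keep the user/non-user and quitter/non-quitter contrasts as adjusted associations. If savings are scaled from them using component effects, state the formula, give the result the same label, and do not attribute it causally to the interventions.

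Cost: a wording change and one more regression, with no new data because the baseline year is already being extracted. The price is wide intervals, about 0.23 to 0.25 SD either side for a main effect before adjustment. Comparing single cells for combinations would be wider still: at the plan's minimum of 15 per cell, 1.96 × √(2/15) = 0.72 SD.

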The Care Manager will also ask if the participant gives the study permission to stay in touch with them and send them reminders about upcoming study contacts during the study via email and/or text message. The Care Manager will remind them that email and text messaging are generally not a secure way to communicate about their health as there are many ways for unauthorized users to access email and text messages. The Care Manager will also inform them that they do not have to provide their email address or text message number to participate in this study.

D. Randomization

Randomization will occur immediately after oral consent and baseline data are collected and will be conducted by healthcare system Tobacco Care Managers using randomization tables developed at UW-CTRI. Randomization will be blocked by clinic, patient-identified gender, and eligibility for randomization to intensive treatment access to ensure equitable distributions across conditions. Enrollees who meet initial eligibility for intensive treatment will be randomized to 1 of 16 conditions (see Table 3), while those who do not meet these criteria (e.g., those with a history of severe renal disease and allergic reaction to NRT) will be randomized to 1 of the first 8 conditions shown below (because the 4th factor, access to intensive treatment, will not apply to them; they will have access to counseling and medication, if appropriate, from the quitline and/or their primary care provider). No placebo will be used in this pragmatic trial. Every enrollee will receive advice to quit smoking and information about resources available to help

them quit smoking no less than 2 times per year for 2 years. All enrollees who want stop-smoking treatment at some point in the 2-year study will have access to no less than a single smoking cessation counseling session and a 2-week supply of a single nicotine replacement therapy (if medically eligible for nicotine medication).

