Aim 1. To develop an optimized package of health system interventions to promote smoking cessation treatment reach among patients not initially willing to quit, logistic regression analyses will be conducted with binary treatment initiation over 1 year of study enrollment as the primary outcome, in the primary sample randomized on all 4 experimental factors. Effect size estimates will be generated and all main and all 2-way, 3-way, and 4-way interactive effects will be tested as predictors in the logistic regression model. In addition, the magnitude of the difference in treatment initiation rates between the most promising intervention conditions and the cell in which all the intervention components are off will be used to generate an upper limit estimate of optimized reach intervention package effects. Exploratory analyses will be conducted adjusted for covariates known to be predictive of treatment use. Exploratory sensitivity analyses will be conducted to estimate intervention component effects across a range of assumptions regarding missing outcome data. We anticipate that 25% of follow-up data will be missing and will examine the robustness of results across intent-to-treat and less stringent assumptions regarding missingness (i.e., that 90%, 80%, or 70% of missing cases are smoking) in sensitivity analyses. We may also use multiple imputation and examine the consistency of results across multiply imputed datasets and those imputed using the simple methods already described. This analysis will use data collected via UW-CTRI staff during follow-up telephone interviews supplemented by data regarding smoking cessation attempts and treatment utilization extracted from the EHR and the WTQL.

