Aim 2. To assess the cumulative main and interactive effects of each intervention component on binary treatment initiation over 2 years of study enrollment, logistic regressions predicting any treatment initiation (defined as completing a first counseling session, the primary outcome at a more distal endpoint) will address this aim, first in the ~240-300 patients (max 300) eligible for intensive treatment to examine all 4 intervention components, and then, separately, in the ~30-60 (max 60) participants who do not meet criteria for access to intensive treatment. As in the analyses for Aim 1, effect coding will be used to ensure the independence of the main and interactive effects in this balanced design, exploratory analyses will be conducted with adjustment for covariates, and exploratory sensitivity analyses will examine the robustness of results across a range of missing data assumptions.

In addition to the binary logistic regression described above, exploratory logistic regression models will estimate intervention component main and interactive effects on treatment completion (all 3 counseling sessions and medication initiation) among those randomly assigned to have access to intensive treatment with C-NRT or varenicline and counseling. This exploratory analysis will quantify the effects of the informational/motivational intervention components on the dose of evidence-based treatment received by participants over 2 years. Effect coding, covariate adjustment, and sensitivity analyses will be used, as described above. Exploratory descriptive analyses of the frequency and temporal patterns of treatment use will also be conducted (e.g., to explore whether C-NRT use tends to follow varenicline more often than the reverse, to see whether C-NRT is more likely to be repeated than varenicline use). As for Aim 1, this analysis will use data collected via UW-CTRI staff during follow-up telephone interviews supplemented by data regarding smoking cessation attempts and treatment utilization extracted from the EHR.

Secondary Aim 1. Although the primary outcome in this study is treatment reach, the ultimate objective of this project is to help more smokers stop smoking. A key secondary binary logistic regression analysis in this project will estimate reach-focused intervention component effects on end-of-study 7-day point-prevalence abstinence confirmed by CO testing, and, if CO is elevated,

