salivary cotinine/anabasine testing, among those claiming abstinence. This analysis will estimate the main and interactive effects of the intervention components on end-of-study (2-year) 7-day point-prevalence abstinence rates (as ascertained by self-report and biochemically confirmed). The primary analysis will be an unadjusted, intent-to-treat analysis, but this will be followed by exploratory adjusted models and sensitivity analyses. This analysis will use data collected by personnel during the final semi-annual follow-up telephone interview plus the biochemical confirmation visit (for those claiming abstinence), supplemented by data on smoking status extracted from the EHR.

Additional, exploratory analyses will examine the 7-day point-prevalence abstinence rates at 3 time points following each round of treatment initiated with the Tobacco Care Managers (3, 12, and 26 weeks post-target-quit-day), for up to 4 rounds of treatment. Exploratory descriptive analyses will summarize abstinence rates at each time point, and the effects of intervention components on these abstinence rates will be explored, both within and across rounds of treatment. This analysis will use data collected by UW-CTRI personnel during the post-quit follow-up telephone interviews.

Secondary Aim 2. The degree to which intervention component effects on abstinence are mediated by treatment use will be examined via formal mediation analysis. These tertiary outcome models will examine the extent to which intervention component effects on 7-day point-prevalence abstinence after 2 years of enrollment are mediated by initiation of treatment in the preceding 2 years. Enrollees eligible for intensive treatment will be the primary sample for these analyses, with exploratory replication in those not eligible for intensive treatment. To examine mechanisms of specific intervention effects on the primary outcomes of interest, additional, exploratory models will examine the extent to which intervention components affect quitting motivation, self-efficacy, and perceived intra-treatment social support, and the degree to which these candidate mediators are associated with treatment initiation and point-prevalence abstinence at the end of the study. Within each treatment episode, the degree to which short-term abstinence (3-, 12-, or 26-weeks postquit) is mediated by reductions in withdrawal will also be explored.

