Supplemental Models. Exploratory GEE models may examine intervention component effects on the pattern of treatment initiation and abstinence across the 4 semi-annual follow-up waves. Additional, exploratory latent class analyses may examine patterns of engagement and abstinence in 6-month epochs over 2 years, conditional on intervention components and combinations. These supplemental analyses will be exploratory and hypothesis generating. Their results may facilitate interpretation of interaction effects in the primary analyses and inform refinement of optimized combinations of reach-focused system interventions.

Covariates. All models described above will be conducted and reported with and without adjustment for healthcare system or clinic and factors known to be associated with treatment engagement (e.g., sex, age, medical comorbidities related to smoking, healthcare utilization⁷³⁻⁷⁷). Covariates will be removed from final adjusted models if not significantly related to the dependent variable to enhance model parsimony.

Power and Sample Size

The target sample size for participants eligible for randomization to intensive treatment access ($N=1664$) was selected based on estimates of the flow of patients through clinics in a 9-month period and the number needed to detect at least an 8% increment in both treatment reach (defined here as initiation or completion of treatment) and 2-year abstinence rates, as we consider 8% to be a clinically meaningful increment in both reach and abstinence. Power estimates for main effects of each intervention component across a range of possible base rates in treatment use (from 5 to 65%) and abstinence (from 5 to 30%) exceed .9 (at alpha .05) with a sample of 1664 participants. Power to detect simple main effects (i.e., to interpret interactions) exceeds .7 for all but one combination of base rates and effect sizes at $N=1664$.

Power will be lower in the sample of smokers who do not meet all eligibility criteria for randomization to intensive treatment access (we estimate this to be roughly 416 participants, but may be as high as 800 participants), but this sample will be sufficiently large to generate

upper-bound estimates of effect sizes for intervention component, component-by-component interaction, and mediator and moderator effects.

July 2022 update to sample size based on recruitment challenges

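### Randomization is blocked by clinic and gender, but neither the unadjusted nor the adjusted version of the reported models is bound to include either factor; the harm is modest and the remedy cheap

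*Combined protocol and SAP*

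**What the plan says.** **Allocation.** Section D, Randomization: "Randomization will be blocked by clinic, patient-identified gender, and eligibility for randomization to intensive treatment access". Section II sets the scale: "Participants (N=240-300) will be recruited in 4-12 primary care clinics in 2 healthcare systems by system staff".

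**Main models.** For Aim 1, "all main and all 2-way, 3-way, and 4-way interactive effects will be tested as predictors in the logistic regression model"; neither clinic nor gender is listed. Adjustment is secondary there: "Exploratory analyses will be conducted adjusted for covariates known to be predictive of treatment use". Aim 2 follows the same pattern: "exploratory analyses will be conducted with adjustment for covariates". For abstinence (Secondary Aim 1) the plan is explicit: "The primary analysis will be an unadjusted, intent-to-treat analysis". Only this last model is called unadjusted outright. For Aims 1 and 2 that status is inferred from the listed terms and from the exploratory label on adjustment.

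**Adjusted models.** The Covariates paragraph says: "All models described above will be conducted and reported with and without adjustment for healthcare system or clinic". Further factors follow as examples, with sex first. It closes with the removal rule: "Covariates will be removed from final adjusted models if not significantly related to the dependent variable to enhance model parsimony". No significance threshold is given, and no covariate is exempt.

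**The concern.** When allocation is balanced within clinic and gender, the usual practice is to keep those factors in at least one prespecified analysis, so that the error bars reflect how patients were allocated. Here no sentence guarantees that. The main models leave both factors out. The adjusted models may use system in place of clinic, may not use the gender variable that defined the blocks, and may lose either factor on a p-value.

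Two things are at stake. The July 2022 sample-size update concedes inadequate power and makes effect sizes and their ranges the main product, so interval width and the choice of model matter more than usual. Also, with the site term, the covariate list and the threshold all open, different outcomes could end up with different adjustment sets chosen after the outcomes are known.

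**Working it through.** **1. The plan's own figure.** The only power statement nearby is power above .9 for an 8-point main effect with 1664 participants, which is 832 per factor level. This point does not rest on it, but it calibrates the formula:

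power = Φ[(Δ − 1.96·s0)/s1], with s0 = √(2p̄(1−p̄)/n) and s1 = √((p1(1−p1)+p2(1−p2))/n).

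- The worst base rate between 5% and 65% is 46%. There s0 = 0.02451 and s1 = 0.02444, so power = Φ[(0.08 − 0.04805)/0.02444] = 0.904. The statement reproduces (two-sided test assumed).
- At the current minimum of 240 (120 per level) with 20% against 28%: s0 = 0.05514, s1 = 0.05489, power = 0.305. This is the unadjusted benchmark for what follows.

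**2. Strata.** With two gender categories, 4 clinics give 8 strata and 12 clinics give 24. Average stratum size runs from 240/24 = 10 to 300/8 = 37.5.

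**3. Simulation inputs.** From the documents: 240 participants, 4-12 clinics in 2 systems, an 8-point increment, alpha .05. Assumed: 8 clinics, 20% base reach, permuted blocks of 16 within clinic by gender, one active component, and effects on the logit scale that are weak (clinic SD 0.2, gender 0.2), moderate (0.5, 0.4) or strong (0.8, 0.4). The model has the four main effects only. There were 20,000 replicates, so Monte Carlo error is about 0.15 points for type I error and 0.33 for power. The adjusted model keeps gender and a site term, with clinics combined within system until each group has at least 5 events and 5 non-events.

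**4. How often the factors go missing** (backward deletion at .05):

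| | Weak | Moderate | Strong |
|---|---|---|---|
| At least one absent from both versions | 98% | 85% | 78% |
| Both absent | 77% | 34% | 12% |
| Site and gender both absent, if system is the site term | 83% | 61% | 53% |

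**5. What that costs:**

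| | Weak | Moderate | Strong |
|---|---|---|---|
| Power, unadjusted | 31.2% | 30.0% | 30.5% |
| Power, factors kept | 32.4% | 31.9% | 33.6% |
| Type I error, unadjusted | 5.2% | 4.5% | 3.9% |
| Type I error, factors kept | 5.6% | 5.0% | 4.6% |
| True SD of risk difference, unadjusted | 0.0548 | 0.0532 | 0.0522 |
| True SD of risk difference, factors kept | 0.0548 | 0.0532 | 0.0521 |
| Reduction in reported SE | 1.7% | 2.8% | 4.5% |
| Coverage, unadjusted | 94.7% | 95.3% | 95.7% |
| Coverage, factors kept | 94.4% | 94.7% | 94.8% |

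Bias of the risk difference is at most 0.1 point in either model. A smaller run (about 4,000 replicates per setting) also gave equal true SDs, with standard errors about 1-3% smaller and a gain of about 1-2 power points.

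**6. How much of the power gain is test size.** Put the unadjusted test at the adjusted model's type I error, with d = z(1−α/2) + z(power):

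- Weak: d = 1.943 − 0.490 = 1.453; at 5.6%, Φ(1.453 − 1.911) = 32.3%, against 32.4%.
- Moderate: d = 2.005 − 0.524 = 1.480; at 5.0%, Φ(1.480 − 1.960) = 31.6%, against 31.9%.
- Strong: d = 2.064 − 0.510 = 1.554; at 4.6%, Φ(1.554 − 1.995) = 33.0%, against 33.6%.

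The size-matched gain is therefore about 0.1, 0.3 and 0.6 points.

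**7. The removal rule alone.** In a separate run of 10,000 replicates with clinics not combined, the rule had power 31.4%, 31.4% and 34.6%, against 32.1%, 31.5% and 33.6% for the fixed model. It costs little power.

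**The case against.** The strongest reply is that the plan already names its main models in advance. Removal by p-value touches only adjusted models, which the aims label exploratory, and every model is promised both ways. Sex is the first covariate named, and the monitoring plan tracks allocation by clinic and sex, so the blocking variables are evident candidates. The missing-factor rates count absence rather than damage, and they are highest where the assumed effects are weakest and omission matters least. The size-matched gain is below one point. With weak effects, adjustment moves type I error from 5.2% to 5.6%, slightly away from 5%.

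All of this stands, and it sets the severity. It does not supply what is missing, which is a sentence requiring either blocking factor to stay in any reported model.

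A reader might infer three stronger points, and none is supported:

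- **That the unadjusted analysis is invalid or inflates false positives.** Its type I error was 3.9-5.2% in the main settings and its risk difference was essentially unbiased.
- **That the main result is selected by p-value.** The removal rule does not reach the unadjusted models.
- **That the rule itself costs material power.** Step 7 shows that it does not.

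**Conclusion.** The gap is real. Clinic and gender define the randomization blocks, and both can be absent from both reported versions of a model. It should be closed, but it does not threaten validity. Adjustment brings the reported standard error closer to the true spread when clinic effects are strong (unadjusted coverage 95.7%, adjusted 94.8%). Across the assumed effects, standard errors shrink by about 2-5% and power rises by about 1-3 points, most of it from test size. The case rests mainly on principle and low cost: design factors should not enter or leave a prespecified model according to their p-values.

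Confidence is medium. The clinic and gender effects and the block size are assumptions. The calculations cover main effects only, not the planned model with all interactions. Other settings (4 or 12 clinics, unequal clinics, 300 participants, base rates of 5% to 65%) gave gains of 0.8-2.4 points, or 0.4-0.9 with healthcare system as the only site term.

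**What to change.** In the Covariates paragraph:

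1. Exempt the blocking factors from significance-based removal.
2. State that every adjusted model includes the gender variable used for blocking and a site term, subject to the exception in item 5.
3. Define site as clinic, with small clinics combined within healthcare system by a rule fixed in advance and blind to condition, or as healthcare system if clinics are too sparse. The rule in the calculations, at least 5 events and 5 non-events per group, is one workable example.
4. Report this version beside the planned unadjusted one, and state in advance which is primary. The sponsor may keep the unadjusted model as primary.
5. Do not add these terms to the full 16-term model where cells have no events. At 15 per cell and 20% reach throughout, the chance of at least one empty cell is already 1 − (1 − 0.8¹⁵)¹⁶ = 44%.

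**Cost.** The change is one of wording, and the blocking variables are collected for every participant. It adds a few parameters and slightly larger small-sample error: type I error on the risk-difference scale was 5.1-6.0%, against 4.3-5.7% unadjusted. Combining sparse clinics is necessary. Separate clinic terms had no finite fit in 0.5%, 3.8% and 15% of simulated trials with 8 clinics (weak, moderate, strong), and in 20% with 12 clinics (moderate). At 5% reach little is gained: with no effect, the rule used in the calculations ended without any site term in 53% of trials.
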